8.1.6 Pregnancy

All pregnancies are to be reported from the time informed consent is signed until the defined follow-up period stated in Section [7.1.5](#).

Any report of pregnancy for any female study participant must be reported within 24 hours to the Shire Pharmacovigilance Department using the Shire Investigational and Marketed Products Pregnancy Report Form. The pregnant female study participant must be withdrawn from the study.

Every effort should be made to gather information regarding the pregnancy outcome and condition of the infant. It is the responsibility of the investigator to obtain this information within 30 calendar days after the initial notification and approximately 30 calendar days post-partum.

Pregnancy complications such as spontaneous abortion/miscarriage or congenital abnormality are considered SAEs and must be reported using the Shire Clinical Trial Serious Adverse Event Form. Note: An elective abortion is not considered an SAE.

In addition to the above, if the investigator determines that the pregnancy meets serious criteria, it must be reported as an SAE using the Shire Clinical Trial Serious Adverse Event Form as well as the Shire Investigational and Marketed Products Pregnancy Report Form. The test date of the first positive serum/urine β -HCG test or ultrasound result will determine the pregnancy onset date.

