Table 3: Double-blind Maintenance Phase

Visit	1 (Screening) ^a	Recommended Telephone call ^b	2 (Baseline) ^a	5	5.1	5.2	6 ^c
Day/Month^d	Day -21 to -3	Day -7 to -4	Week 0	Weeks 2-4	Week 13	Week 26/ Withdrawal	Follow-up
Review DUCS instructions, ability to read and understand e-diary with subject/caregiver	✓						
Subject/caregiver e-diary entry: rectal bleeding, stool frequency, DUCS _h and Overall Current Health ^h	✓		✓		✓	✓	
Assessment of e-diary compliance ^a		✓					
Global Change in Health ⁱ						✓	
IMPACT III ⁱ			✓			✓	
PUCAI (where applicable)			✓			✓	
Average stool frequency ^{j, k, l}			✓		✓	✓	
Average rectal bleeding ^{j, k, l}			✓		✓	✓	
PGA ^{k, l}			✓			✓	
Endoscopy (flexible sigmoidoscopy or colonoscopy) for study eligibility ^{d, l, m}	✓		✓				
Endoscopy (flexible sigmoidoscopy or colonoscopy), where possible ^j						✓	
IRT entry	✓		✓	✓	✓	✓	
Calculate partial UC-DAI			✓			✓	
Investigational product dispensed			✓	✓	✓		
Investigational product collected and compliance calculated				✓	✓	✓	
Adverse events	✓	✓	✓	✓	✓	✓	✓
Concomitant medication	✓		✓		✓	✓	✓

Table 3: Double-blind Maintenance Phase

Visit	1 (Screening) ^a	Recommended Telephone call ^b	2 (Baseline) ^a	5	5.1	5.2	6 ^c
Day/Month ^d	Day -21 to -3	Day -7 to -4	Week 0	Weeks 2-4	Week 13	Week 26/ Withdrawal	Follow-up

Abbreviations: DUCS=Daily Ulcerative Colitis Scale for children and caregivers; eCRF=electronic case report form; e-diary=electronic diary; IRT=interactive response technology; PGA=Physician's Global Assessment; PUCAI=Pediatric Ulcerative Colitis Activity Index; UC-DAI=Ulcerative Colitis Disease Activity Index.

^a The Screening Visit (Visit 1) and the Baseline Visit (Visit 2) in Table 3 apply only to subjects entering directly into the Double-blind Maintenance Phase.

^b Approximately 4 to 7 days prior to the Baseline Visit (Visit 2) and prior to each subsequent visit (Visits 5, 5.1, and 5.2), it is recommended that site staff telephone the subject or the subject's caregiver to remind them to enter UC-DAI symptoms (rectal bleeding and stool frequency) into the e-diary every night, even if the subject has no symptoms.

^c Follow-up assessment may be performed via telephone call within 7 days of the last dose of investigational product.

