4.4 Reproductive Potential

4.4.1 Female Contraception

Sexually active females of childbearing potential must be using an acceptable form of contraception. Females of childbearing potential must be advised to use acceptable contraceptives throughout the study period and for 30 days following the last dose of investigational product. If hormonal contraceptives are used they should be administered according to the package insert.

Females of childbearing potential who are not currently sexually active must agree to use acceptable contraception, as defined below, if they become sexually active during the period of the study and 30 days following the last dose of investigational product.

All female subjects of childbearing potential must have a negative serum beta-human chorionic gonadotropin (β -HCG) pregnancy test at the Screening Visit (Visit 1) and prior to randomization. Female subjects of childbearing potential must abstain from sexual activity that could result in pregnancy or agree to use acceptable methods of contraception. Abstinence can only be accepted if this is true abstinence in line with the preferred and usual lifestyle of the subject.

Acceptable methods of contraception are:

- Intrauterine devices plus condoms
- Double-barrier methods (eg, condoms and diaphragms with spermicidal gel or foam)
- Hormonal contraceptives (oral, depot, patch, injectable, or vaginal ring), stabilized for at least 30 days prior to the Screening Visit (Visit 1), plus condoms. Note: if subject becomes sexually active during the study, they must use 1 of the other acceptable methods noted above in addition to the hormonal contraceptive until it has been stabilized for 30 days.

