7.1.5 Follow-up Period (Visit 6)

The follow-up period for this protocol is 7 days following last dose of investigational product. All subjects, whether they have completed the study or withdrawn early, must have a follow-up contact.

At the end of this period there will be a visit or telephone call initiated by the site staff to query for SAEs, AEs, and concomitant treatments. All AEs and SAEs that are not resolved at the time of this contact will be followed to closure (see Section [8](#)).

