7.2.2.7 Pregnancy Test

A serum β -HCG pregnancy test is performed for all females of childbearing potential at the following visits as applicable to the subject's participation in the study:

- Screening Visit (Visit 1)
- Double-blind Acute Phase: Week 8 (Visit 3.2)
- Open-label Acute Phase: Week 8 (Visit 4.2)
- Double-blind Maintenance Phase: Week 26 (Visit 5.2)
- If pregnancy is suspected
- On withdrawal of the subject from the study.

A urine pregnancy test is performed for all females of childbearing potential at all other visits as indicated in [Table 1](#), [Table 2](#), and [Table 3](#).

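### Required pregnancy reporting stops 7 days after the last dose, while the contraception requirement runs to 30 days, so 23 of the 30 post-dose days fall outside the required reporting window

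*Protocol*

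**What the plan says.** Four parts of the protocol bear on this.

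- **Reporting window (8.1.6).** "All pregnancies are to be reported from the time informed consent is signed until the defined follow-up period stated in Section" (the section cited is 7.1.5).
- **Length of that window (7.1.5).** "The follow-up period for this protocol is 7 days following last dose of investigational product".
- **Contraception (4.4.1).** Of female participants who could become pregnant, it says that they "must be advised to use acceptable contraceptives throughout the study period and for 30 days following the last dose of investigational product".
- **Dating (8.1.6).** The date of the first positive serum or urine β-HCG "test or ultrasound result will determine the pregnancy onset date".

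The arrangements around the end of treatment are as follows. Section 7.2.2.7 schedules serum tests at screening and at the final visit of each phase (Visits 3.2, 4.2 and 5.2), whenever pregnancy is suspected, and "On withdrawal of the subject from the study". The schedules of assessments (Tables 1 to 3) show no pregnancy test at Visit 6. In 7.1.5 the purpose of the Visit 6 contact is "to query for SAEs, AEs, and concomitant treatments"; pregnancy is not named. Footnote c to Table 3 adds: "Follow-up assessment may be performed via telephone call within 7 days of the last dose of investigational product".

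Two further provisions extend past day 7. Section 8.1.6 sets a 24-hour deadline for passing on any report of pregnancy, with no end date in that sentence. It also classes miscarriage and congenital abnormality as SAEs. Section 8.2.4 keeps related SAEs reportable whenever the investigator learns of them after the study.

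**The concern.** The protocol treats the 30 days after the last dose as time in which pregnancy should be avoided, yet its required reporting of pregnancies ends on day 7. Nothing in either document explains the difference.

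The dating rule adds to it. A pregnancy conceived while the drug was still being taken, but first tested positive on day 8 or later, has an onset date after the window closes.

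What is at stake is safety information. Outcome follow-up in 8.1.6 is timed from the initial notification, so a pregnancy that is never notified contributes no outcome. If late pregnancies surface mainly through complications, the sponsor would see those without the uncomplicated pregnancies needed to interpret them.

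**Working it through.** The documents state no figure to reproduce; the check is date arithmetic.

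**Inputs from the protocol:** follow-up F = 7 days (7.1.5); post-dose contraception C = 30 days (4.4.1); time on treatment T = 8 weeks (56 days) for the Double-blind Acute Phase, 26 weeks (182 days) for the Double-blind Maintenance Phase, and at most about 42 weeks (294 days, 3.2). A 2-week case (14 days) represents early withdrawal.

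**Assumptions not in the documents:** the lag L from conception to first positive test is between 0 and 28 days, and conceptions are spread evenly over time.

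**Step 1. Post-dose days outside required reporting, by test date.**
C − F = 30 − 7 = 23 days; 23/30 = 77%.

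**Step 2. The same by conception date.** Let c be the conception day relative to the last dose (day 0). The onset date is c + L, which is outside the window when c + L > 7. Once L is 7 days or more, every conception after the last dose is dated outside.

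**Step 3. Conceptions during dosing.** These are dated outside only when L > 7, and then for the last L − 7 days of dosing:

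- L = 10: 10 − 7 = 3 days
- L = 14: 14 − 7 = 7 days
- L = 28: 28 − 7 = 21 days

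This is generous to the protocol. It credits detection up to day 7, although no pregnancy test is scheduled after the final visit.

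**Step 4. Share of treatment plus 30 days.** The contraception requirement also covers the study period. Days dated outside are 23 + L (capped at T + 30), so the share is (23 + L)/(T + 30):

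| Treatment | T + 30 | L = 0 (23 days) | L = 14 (37 days) | L = 28 (51 days) |
|---|---|---|---|---|
| 42 weeks | 324 | 7% | 11% | 16% |
| 26 weeks | 212 | 11% | 17% | 24% |
| 8 weeks | 86 | 27% | 43% | 59% |
| 2 weeks | 44 | 52% | 84% | 100% (capped at 44) |

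**Step 5. Would a longer window alone be enough?** If reporting ran to day 30 by test date, Step 1 falls from 23 days to 0. Conceptions in the last L days of the 30 would still be dated after it (14 days if L = 14). Basing reportability on estimated conception date removes that remainder.

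**The case against.** The strongest reply is that later pregnancies are not shut out. The 24-hour sentence in 8.1.6 has no end date. Miscarriage and congenital abnormality count as SAEs, as does a pregnancy that itself meets serious criteria, and 8.2.4 leaves related SAEs reportable without limit. The dating sentence says how to fix an onset date; it does not exempt a pregnancy dated after day 7. Serum testing is also required at each phase's final visit, on withdrawal and on suspicion, which will find many on-treatment conceptions in time.

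Much of this stands. A reader might infer that pregnancies recognised after day 7 are not reportable at all and can produce no outcome data; the documents do not go that far, for the reasons just given. A reader might also infer that most pregnancies in the contraception period are missed. The 77% applies only to the 30 post-dose days. Over treatment plus 30 days the share is a minority for 26 or 42 weeks of treatment (7% to 24%); it passes half at every assumed lag only for very short exposure. Nor does 4.4.1 define a fetal-risk period; it states a contraception requirement.

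These routes still do not close the gap. The 24-hour sentence acts only when someone volunteers a report, and the sentence after it, on withdrawing the pregnant participant, presumes she is still in the study. Uncomplicated pregnancies that meet no serious criterion, elective abortions and events judged unrelated fall outside the SAE route. No procedure obliges the site to ask about pregnancy after the final visit.

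**Conclusion.** The mismatch is real and rests on the text alone: required reporting covers 7 of the 30 post-dose days and leaves 23 (77%) outside. That some conceptions during dosing may also be dated outside is a conditional addition. It needs a detection lag above 7 days, an assumption the documents neither give nor contradict, and it reaches about the last 3, 7 or 21 days of dosing at lags of 10, 14 or 28 days.

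The practical size is small. The documents give no pregnancy rate; the participants are aged 5 to 17 at entry, and only some are females of childbearing potential. No efficacy endpoint or planned analysis depends on it. It is a gap in safety capture, worth correcting because the correction is cheap.

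**What to change.** Reconcile 8.1.6 with 4.4.1, leaving the contraception requirement as it is:

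1. In 8.1.6, replace the cross-reference to 7.1.5 with a reporting window that matches the post-dose period stated in 4.4.1.
2. In the same section, make a pregnancy reportable when its estimated conception falls between the first dose and the end of that period, whatever the date of the first positive test.
3. At the Visit 6 contact, ask females of childbearing potential, or their caregivers, to report any such pregnancy.

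The cost is two sentences in 8.1.6 and one line in the Visit 6 script. No visit or test is added. The downside is an occasional late report to process.

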8.1.7 Abuse, Misuse, Overdose, and Medication Error

Abuse, misuse, overdose, or medication error (as defined below) must be reported to the sponsor according to the SAE reporting procedure whether or not they result in an AE/SAE as described in Section [8.2](#). Note: The 24-hour reporting requirement for SAEs does not apply to reports of abuse, misuse, overdose, or medication errors unless these result in an SAE.

The categories below are not mutually exclusive; the event can meet more than 1 category.

- **Abuse** – Persistent or sporadic intentional intake of investigational product when used for a non-medical purpose (eg, to alter one's state of consciousness or get high) in a manner that may be detrimental to the individual and/or society
- **Misuse** – Intentional use of investigational product other than as directed or indicated at any dose (Note: this includes a situation where the investigational product is not used as directed at the dose prescribed by the protocol)
- **Overdose** – Intentional or unintentional intake of a dose of an investigational product exceeding a pre-specified total daily dose of 4.8g of the product
- **Medication Error** – An error made in prescribing, dispensing, administration, and/or use of an investigational product. For studies, medication errors are reportable to the sponsor only as defined below.

Cases of subjects missing doses of the investigational product are not considered reportable as medication errors.

Medication errors should be collected/reported for all products under investigation.

The administration and/or use of the unassigned treatment is/are always reportable as a medication error.

The administration and/or use of an expired investigational product should be considered as a reportable medication error.

All investigational product provided to pediatric subjects should be supervised by the parent/LAR/caregiver.

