Subjects without a clinical response after completion of treatment in both the Double-blind Acute Phase and the Open-label Acute Phase will not be eligible to enter the Double-blind Maintenance Phase and must be withdrawn.

Subjects may enter the Double-blind Maintenance Phase directly following the Baseline Visit (Visit 2) if they have a partial UC-DAI ≤ 1 (with rectal bleeding=0 **and** stool frequency ≤ 1 **and** PGA=0) **and** with mucosal appearance (endoscopy score)=0 or 1 at that visit.

MMX mesalamine/mesalazine is dosed once daily by mouth. The selection of doses in this study is based on an approximate average of 43mg/kg for the low dose and 85mg/kg for the high dose in the 3 lower weight groups (18 to ≤ 23 kg, >23 to ≤ 35 kg and >35 to ≤ 50 kg). These doses were selected based on standard of care dosing for other 5-ASA products in the pediatric population and pharmacokinetic dosing results. The dosing for the highest weight group (>50 to ≤ 90 kg) is based on adult UC experience.

This study will be conducted in children and adolescents (aged 5-17 years) to collect data on the safety and efficacy of MMX mesalamine/mesalazine in this population. This study is a Pediatric Research Equity Act post-approval commitment with the US FDA.

[figure not shown]
Minimum enrollment criteria have been agreed with FDA as follows, based on subject weight group; these are summarized in [Table 4](#).

Table 4: Minimally Required Number of Subjects per Weight Group

Weight Group	Number of Subjects in Combined Low and High Dose ^a
18 to ≤ 23 kg	2
>23 to ≤ 35 kg	12
>35 to ≤ 50 kg	18
>50 to ≤ 90 kg	36

^a Randomization will be stratified by weight group with the aim of creating balance between the 2 dose groups within a weight group.

Figure 1: Study Design Flow Chart

PGA=Physician's Global Assessment; UC-DAI=Ulcerative Colitis Disease Activity Index

^a Subjects with partial UC-DAI ≥ 2 (with a combined rectal bleeding **and** stool frequency score ≥ 1 **and** PGA=1 or 2) **and** with mucosal appearance (endoscopy score)=2 or 3.

^b Subjects with partial UC-DAI ≤ 1 (with rectal bleeding=0 **and** stool frequency ≤ 1 **and** PGA=0) **and** with mucosal appearance (endoscopy score)=0 or 1.

Notes: Solid boxes indicate study phases. Dashed ellipses indicate decision points.

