6.2.3 Dosing

Subjects entering the Double-blind Acute Phase or entering the Double-blind Maintenance Phase directly will be randomized to low- or high-dose MMX mesalamine/mesalazine stratified by their weight group at the Baseline Visit (Visit 2).

Subjects entering the Double-blind Maintenance Phase after completing 1 or both of the Acute Phases will be re-randomized to low- or high-dose MMX mesalamine/mesalazine at the start of the Double-blind Maintenance Phase at Visit 3.2 (Week 8 of the Double-blind Acute Phase) or 4.2 (Week 8 of the Open-label Acute Phase), as applicable, based on their weight at the time of re-randomization.

Doses will be as follows:

- 900 or 1800mg/day for subjects weighing 18 to \leq 23kg
- 1200 or 2400mg/day for subjects weighing >23 to \leq 35kg
- 1800 or 3600mg/day for subjects weighing >35 to \leq 50kg
- 2400 or 4800mg/day for subjects weighing >50 to \leq 90kg.

Subjects participating in the Open-label Acute Phase will receive the high dose for their weight group. The subject's weight at Visit 3.2 (Week 8/Withdrawal of the Double-blind Acute Phase) will be used to determine the high dose assigned to the subject.

Investigational product will be administered orally, once daily, in accordance with the MMX Mesalazine (Mesalamine) Investigator's Brochure. No titration or dose adjustment is allowed.

Dosing with investigational product will begin the day of the Baseline Visit (Visit 2) if the subject's currently prescribed 5-ASA treatment (if applicable) has not yet been taken that day. If the subject's currently prescribed 5-ASA treatment (if applicable) has been taken the day of the Baseline Visit (Visit 2), dosing with investigational product will begin the day after the Baseline Visit (Visit 2).

When proceeding through study phases, dosing with newly prescribed investigational product will begin the day of the study visit if the subject's currently prescribed investigational product from the current phase has not yet been taken that day. If the subject's currently prescribed investigational treatment has been taken the day of the study visit, dosing with newly prescribed investigational product will begin the day after the first study visit of the new phase.

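### Protocol 8.1.7 sets one overdose limit (>4.8 g/day) for all weights, so an accidental double high dose in children up to 35 kg is not an overdose, and the medication-error text leaves its reporting unclear

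*Protocol*

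**What the plan says.** Protocol 8.1.7 requires abuse, misuse, overdose and medication error to reach the sponsor even when no adverse event follows. Overdose is "Intentional or unintentional intake of a dose of an investigational product exceeding a pre-specified total daily dose of 4.8g of the product". The figure has no weight qualifier, and the SAP gives no overdose definition of its own.

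Protocol 6.2.3 doses by weight group. The list runs from "900 or 1800mg/day for subjects weighing 18 to" and including 23 kg, up to "2400 or 4800mg/day for subjects weighing >50 to" and including 90 kg. The two groups between have high doses of 2400 and 3600 mg/day. In addition, "Subjects participating in the Open-label Acute Phase will receive the high dose for their weight group". Section 3.1 bases the doses on "an approximate average of 43mg/kg for the low dose and 85mg/kg for the high dose in the 3 lower weight groups"; the heaviest group follows adult experience.

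The other categories in 8.1.7 matter here. Misuse is confined to intentional departures from instructions. Medication error covers mistakes at any step from prescribing to taking the product, and one line says "Medication errors should be collected/reported for all products under investigation". But the definition closes with "For studies, medication errors are reportable to the sponsor only as defined below". The lines that follow exclude missed doses and name unassigned treatment and expired product as reportable. None mentions extra intake of the child's own assigned product.

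**The concern.** A single gram limit does not fit a trial whose doses rise with weight. In the lighter children, intake can go well above the highest dose the plan assigns to them and still fall short of the overdose definition. If the excess was accidental, misuse does not apply either, and only the medication-error text is left to catch it.

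What is at stake is safety capture. Section 8.1.7 wants symptom-free events reported, so adverse event collection is not a full substitute. In the three lighter groups, whether an accidental excess of up to 4.8 g with no symptoms becomes a safety report depends on how a site reads the medication-error lines. No efficacy result is involved.

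**Working it through.** **Inputs.** Overdose limit T = 4800 mg, and intake must exceed it (Protocol 8.1.7). High doses H = 1800, 2400, 3600 and 4800 mg/day (Protocol 6.2.3). Minimum subjects per weight group, both doses combined, 2, 12, 18 and 36 (Protocol 3.1, Table 4).

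**Origin of the limit.** T equals H in the heaviest group (4800/4800 = 1.0) and in no other.

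**Limit against each group's own high dose.** Compute T/H, then test whether 2H > T. The mg/kg range divides 2H by the upper and lower weight bounds of the group.

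| Weight group | H (mg) | T/H | 2H (mg) | 2H > 4800? | 2H in mg/kg |
|---|---|---|---|---|---|
| 18 to ≤23 kg | 1800 | 2.67 | 3600 | No | 3600/23 = 157 to 3600/18 = 200 |
| >23 to ≤35 kg | 2400 | 2.00 | 4800 | No (equal) | 4800/35 = 137 to 4800/23 = 209 |
| >35 to ≤50 kg | 3600 | 1.33 | 7200 | Yes | 7200/50 = 144 to 7200/35 = 206 |
| >50 to ≤90 kg | 4800 | 1.00 | 9600 | Yes | 9600/90 = 107 to 9600/50 = 192 |

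A double high dose is therefore an overdose in two of four groups. At >35 to ≤50 kg the double dose is caught, but intake above 3600 mg up to 4800 mg is not.

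**Against assigned exposure.** The largest high dose per kg anywhere in the plan is 2400/23 = 104 mg/kg.

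**Group size.** Section 3.1 introduces Table 4 with "Minimum enrollment criteria have been agreed with FDA as follows, based on subject weight group". The minimum total is 2 + 12 + 18 + 36 = 68. The two groups where a double high dose escapes hold 2 + 12 = 14, and 14/68 = 21% of the minimum.

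**Would compliance data show it?** SAP 5.6.2 divides tablets taken over a whole phase by tablets due, with 80–120% as the middle category. One doubled day in 8 weeks gives 57/56 = 101.8%; in 26 weeks it gives 183/182 = 100.5%. Eleven doubled days in 8 weeks give 67/56 = 119.6% and twelve give 68/56 = 121.4%, so twelve are needed to pass 120%, and any missed day offsets a doubled one.

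**With weight-group limits.** Limits of >1.8, >2.4, >3.6 and >4.8 g/day would make a double high dose (3.6, 4.8, 7.2 and 9.6 g) an overdose in all four groups. A doubled low dose equals the group's high dose and would still not be one.

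**The case against.** The strongest reply is that 8.1.7 already covers the event. Its opening makes medication errors reportable, and the definition takes in errors of administration and use, which an accidental double dose plainly is. The exclusion of missed doses would serve no purpose if only unassigned and expired product counted. The sentence on all products is itself among the lines that follow the limiting sentence. This is the better reading and it stands. It does not remove the limiting sentence, though, and a site could reasonably take the two named cases as the full list. Nor does it correct the overdose definition.

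Second, little is left uncovered. Intentional excess is misuse, adverse events are collected, caregivers supervise dosing, and tablets are counted at visits. That stands too, and it limits the gap to accidental, symptom-free excess. But Protocol 6.5 answers a dosing discrepancy with re-education, and phase-level compliance barely moves after one doubled day. Neither is a safety report.

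Third, the Investigator's Brochure, which is the reference safety document (8.2.1), may explain 4.8 g. It is not among the documents, so the limit cannot be called unsafe.

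Fourth, sites cannot apply a mg limit under the blind, because tablets match in number and size between arms within a weight group (Protocol 6.1.1). This stands. A reporting rule based on tablet count has to do most of the work, and the weight-group limit supports it.

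**Conclusion.** The overdose definition misclassifies accidental excess in the three lighter groups, most clearly a double high dose up to 35 kg, and the medication-error wording does not settle whether such an event must be reported. This is a minor point and a cheap improvement.

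Four stronger inferences are not supported:

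- **That these events go unreported.** The medication-error definition probably covers them; the text is unclear, not silent.
- **That lighter children are exposed to known harm.** The documents state no toxic level and show no harm.
- **That 21% of subjects are affected.** The 14 of 68 comes from minimum quotas. SAP 3.5 puts the acute phase at 53 subjects and the maintenance phase at 80 or more. Halving the 14 for 1:1 allocation does not help, because acute-phase responders are re-randomized and open-label entrants all take the high dose. The affected share cannot be estimated from the documents.
- **That a doubled dose reaches 267 mg/kg.** That is 4800/18, which takes 2.67 times the high dose. A double high dose in the lightest group is 157–200 mg/kg.

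The conclusion rests on reading the 4.8 g limit as applying to every subject, which is how it is written.

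**What to change.** Two changes to Protocol 8.1.7:

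1. Add a line making accidental intake of the subject's own product above the assigned daily amount a reportable medication error. In the double-blind phases this means more than the assigned tablets in a day, in either arm. In the open-label phase it means more than the assigned mg. Sites then report a tablet count, and no code break is needed for reporting.
2. Replace the flat 4.8 g with the high dose of the subject's weight group: >1.8, >2.4, >3.6 and >4.8 g/day. Apply it directly in the open-label phase. In the double-blind phases the sponsor applies it after unblinding, so that extra placebo or low-arm tablets are not mislabelled as overdose.

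The cost is one definition, one line and a memo to sites. There would be a few more non-serious reports, which 8.1.7 exempts from the 24-hour rule unless an SAE results. In the blinded phases the mg label comes late, and it may be only a range when part of a low-arm day's tablets (active plus placebo) was taken in excess.
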